10.4. Evaluation of Response to Treatment (ERT)

For each treatment visit, an Evaluation of Response to Treatment (ERT) will be performed (in clinic) at each visit, including 48 hours after first dose in Part A only and 24-hour, 7 Day, and 14 Day post treatment (by phone). ERT data will be presented in listings.

10.5. Provider Questionnaire

At the EOT visit, a 9-question Provider Questionnaire will be completed. Questions will include ease of use of the applicator and general experiences. Responses to the questions will be displayed in subject listings. No summary tables of the questionnaire are planned.

10.6. Vital Signs

Heart rate and temperature will be collected at each in clinic visit. Change from baseline will be calculated for each post baseline visit temperature and pulse rate. Height and weight will be recorded at screening and follow-up visits (including EOT).

Summary statistics for each vital sign and change from baseline result will be displayed by treatment group and visit for temperature and pulse rate. By-visit summaries will utilize visit windows as discussed in Section 8. Baseline height and weight will be summarized as part of the baseline summary. Any other collection of height and weight will be included in the data listing.

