4.2 Nonclinical Studies

Cantharidin is a potent inhibitor of protein phosphatases that are found in all tissues.^[10] The inhibition of these phosphatases may be involved in cantharidin's systemic manifestations when delivered orally or via injection (Section 6.1.1 of the Investigator's Brochure [IB]). The available nonclinical studies to assess the potential for untoward pharmacodynamic effects of cantharidin with systemic exposure have largely focused on the cardiovascular system. With acute systemic exposure of rats to oral dosing with 6.9 mg/kg (41.4 mg/m²) of cantharidin, cardiac waveform and function were adversely affected, likely related to its inhibitory effect on protein phosphatases.^[11] Cantharidin is a vasoconstrictor and may also be responsible for decreases in urine volume with single oral dose administration.^[11, 12] However, it is possible that cantharidin may have a direct effect on the renal vascular and tubular epithelium via its inhibitory action on protein phosphatases. Cantharidin may also have an effect on central nervous system function,^[11] although it is unclear whether noted decreases in locomotion and reduced body temperature were secondary to the cardiovascular manifestations noted with the high doses.

Information available on the pharmacokinetics and metabolism of cantharidin showed that oral absorption of cantharidin in rats and dogs is rapid but incomplete, with peak systemic exposures occurring by 2 hours in rats (Section 6.2 of the IB).^[13] The apparent plasma elimination half-life of cantharidin was about 20 minutes in dogs.^[14] Tissue distribution of cantharidin was ubiquitous, consistent with the widespread distribution of protein phosphatases.

Nonclinical toxicity information available on cantharidin is predominantly from single dose (acute) studies by the dermal, oral, intraperitoneal, and intravenous (IV) routes of administration (Section 6.3 of the IB). The only adverse findings associated with acute dermal exposure to cantharidin in animals were local irritation and skin blistering. No systemic toxicity was noted by this route in animals.

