Treatment with VP-102 was well-tolerated. A total of 29 subjects (88%) reported at least one treatment-emergent adverse event (TEAE), including expected LSRs such as blistering or erythema. Most subjects had mild TEAEs; 3 subjects had moderate TEAEs. Overall, 21 (63.6%) subjects had TEAEs related to study drug, most of which were LSRs. There were no serious adverse events (SAEs) or TEAEs leading to premature study withdrawal.

Treatment with VP-102 was associated with significantly reduced lesion count, improved QoL, and complete clearance of MC lesions. Sixteen (16) subjects (48.5%) achieved complete clearance of all MC lesions on or before Week 12. The median lesion count was reduced 98% from baseline to Week 12. Decreases in mean CDLQI composite scores were observed, from 2.58 (standard deviation = 3.446) at baseline to

0.38 (standard deviation =0.871) at Week 12. No subjects reported spread of molluscum lesions to any siblings during the study.

Plasma drug levels were below the limit of quantitation in 65 of 66 samples. In one subject, the level was slightly above the lower limit of quantitation 2 hours after VP-102 application but was not detectable at 6 and 24 hours. Importantly, no systemic cantharidin was detected in the patient with the highest number of lesions (113 lesions treated) nor in the two subjects with genital involvement.

In a separate double-blind, Phase 2 study (12-01-004), topical cantharidin (0.7% w/v) was well tolerated and associated with the clearance of MC in 94 subjects with childhood molluscum.^[15]

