or has not acted as, the Blinded Assessor for the subject throughout the subject's participation

- Warts that develop in areas that are unable to be treated, (e.g., close to a mucous membrane) will not be evaluated, documented, or considered in the analysis
- Photography
 - Subjects who previously agreed to participate in the photographic portion of the study will have photographs of warts taken by the study team
 - If there are no warts remaining, the same areas will be photographed regardless of whether warts are present
- Assess, identify, and record any new AEs
- Record any new concomitant medications
- Complete study completion form for all subjects (Study Day 147 (EOS) Visit only)

9.6 **Unscheduled Visit**

In the event that any post-treatment LSR presents a safety concern (including but not limited to severe blistering, ulceration, edema, or pain), an “Unscheduled” clinic visit must be scheduled and the subject assessed accordingly. In addition, if any post-treatment AEs present a safety concern, the subject may be brought in for an unscheduled visit. “Unscheduled” visits should also be used for visits in which treatment is unable to be applied to all warts due to ongoing LSRs.

Subjects will return to the clinical site and the following evaluations will be performed and recorded in the eCRF.

- Clinical assessments
 - Measure vital signs (temperature, heart rate)
 - Record reason why study drug was not administered at treatment visit (if applicable)

-
- Dermatologic exam by anatomical location
 - Conducted by a study team member who is not considered, or has not acted as, the Blinded Assessor for the subject throughout the subject's participation
 - ERT assessment
 - Only collect new information since the last contact
 - All ERT safety assessments must be conducted and recorded on ERT by a qualified member of the research team before study drug application; ERT assessments must be conducted by a study team member who is not considered, or has not acted as, the Blinded Assessor for the subject throughout the subject's participation
 - Warts that develop in areas that are unable to be treated, (e.g., close to a mucous membrane) will not be evaluated, documented, or considered in the analysis
 - Photography
 - Subjects who previously agreed to participate in the photographic portion of the study will have photographs of warts taken by the study team
 - Assess, identify, and record any new AEs
 - Record any new concomitant medications

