12.4 Safety Analyses

Safety analyses will be conducted in the Safety Population by actual treatment received.

Adverse events, including LSRs, will be coded with the Medical Dictionary for Regulatory Activities (MedDRA[®]) Version 20.0. The number and percentage of subjects having TEAEs will be tabulated by system organ class and MedDRA preferred term with a breakdown by treatment group. A subject-by-subject AEs data listing, including verbatim term, preferred term, treatment, severity, location, and causal relationship to the study drug will be provided. The number of subjects experiencing TEAEs and number of TEAEs will be summarized by treatment using frequency counts.

Any AE with an onset date after the EOS visit will be considered off study and will not be included in tables summaries (although they will appear in AE listings). Each AE will be counted only once for a given subject. If the same AE occurs on multiple occasions for a subject, the occurrence with the highest severity and relationship to study drug will be reported. If two or more AEs are reported as a unit, the individual terms will be reported as separate events.

Changes in vital signs (temperature and heart rate), from baseline to EOS, will be examined. Treatment-emergent changes from normal values to abnormal values will be identified.

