On the Wart Count case report form (CRF), the total number of overall EGW warts is collected. Genital warts that develop in areas that are unable to be treated or other types of warts will not be evaluated, documented, or considered in the analysis.

Some efficacy endpoints will be summarized by treatment visit. Treatments are planned to occur every 21 (+/- 4) days as long as warts are present for up to 4 treatments within the 75 day treatment period. Treatment may be delayed for various reasons, including but not limited to ongoing LSRs. As a result, the timing of when subjects receive treatment may vary. For the purpose of summarizing treatment visits, only visits when treatment was given will be considered. Moreover, a window will be applied to each visit to ensure that subjects are compared at the same treatment durations. A window of +/- 10 days from the targeted treatment schedule will be used. The table below summarizes the windows. These windows will be used on all by-visit summaries.

Visit	Target Day	Window
1	1	N/A
2	21	11 – 31
3	42	32 – 52
4	63	53 – 73
Day 84 EOT	84	74 – 94
Follow-up Day 112	112	95 – 129
Follow-up Day 147	147	130 – 157

If more than one visit falls within a window, then the visit closest to the target day will be used in the analysis. Visits when treatment was planned but treatment was not applied will be recorded as “Unscheduled”. Unscheduled visit information will not be considered for by-treatment visit summary tables. However, all efficacy data will be presented in data listings.

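### SAP 10.6 omits the normal-to-abnormal vital-signs analysis that Protocol 12.4 requires, and its visit windows leave the Part A 48-hour readings out of every by-visit table

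*SAP*

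**What the plan says.** Protocol 12.4 sets two vital-signs analyses. The first is change over the study: "Changes in vital signs (temperature and heart rate), from baseline to EOS, will be examined". The second is at subject level: "Treatment-emergent changes from normal values to abnormal values will be identified".

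SAP 10.6 covers the first: "Summary statistics for each vital sign and change from baseline result will be displayed by treatment group and visit for temperature and pulse rate". SAP Section 5 defines the statistics for continuous variables as mean, standard deviation, median, minimum and maximum. For timing, SAP 10.6 refers to the efficacy section: "By-visit summaries will utilize visit windows as discussed in Section 8". SAP Section 8 applies its windows to every by-visit summary. It counts a treatment visit only if treatment was given, and adds: "Unscheduled visit information will not be considered for by-treatment visit summary tables".

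The protocol collects vital signs at visits that these rules do not cover. Protocol 9.3.1.3 measures temperature and heart rate at the in-person visit 48 (±8) hours after the first application, in Part A only. Protocol 9.6 measures them at unscheduled visits, and such a visit is mandatory in one case: "In the event that any post-treatment LSR presents a safety concern".

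**The concern.** Vital signs are named in the secondary safety objective of both documents. The SAP introduction makes the SAP's analyses the basis of the study report, so an analysis missing from the SAP is likely to be missing from the report. SAP 10.6 has no shift or abnormality summary and no reference ranges, and gives no reason for leaving them out.

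The windows add to this. The 48-hour visit is the only scheduled vital-signs assessment soon after dosing, and it is the time point on which the Part A primary safety objective rests. The scheduled readings at Treatment Visits 2 to 4 are taken before application, normally 17 to 25 days after the previous one. The remaining scheduled readings are at Day 84 and later. A reader of the planned tables could not tell how many subjects moved from normal to abnormal, and would see none of the early post-dose readings.

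**Working it through.** The documents give no figure on this point, so there is nothing to reproduce. The check sets the two plans side by side and then maps visit days onto the windows.

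**1. Analyses required and planned**

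| Analysis | Protocol 12.4 | SAP 10.6 |
|---|---|---|
| Change from baseline | Required | Planned, by visit |
| Normal-to-abnormal changes | Required | Absent |
| Reference ranges | Not given | Not given |

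**2. Windows (SAP Section 8)**

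Visit 1 is Day 1, with no window. The others are Visit 2, Days 11–31; Visit 3, Days 32–52; Visit 4, Days 53–73; EOT, Days 74–94; Day 112 visit, Days 95–129; Day 147 visit, Days 130–157. Coverage is continuous from Day 11 to Day 157. The gap is Days 2 to 10, which is 10 − 2 + 1 = 9 days.

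**3. The Part A 48-hour visit**

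The visit takes place 48 − 8 = 40 to 48 + 8 = 56 hours after an application on Day 1. Depending on the clock time of application, that is Study Day 2, 3 or 4. All three lie in the gap, so none of these readings has a row in a by-visit table. The planned number is 3 groups × 6 = 18 subjects, of whom 3 × 5 = 15 are on VP-102 and 3 × 1 = 3 on placebo.

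**4. Unscheduled visits**

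- After Treatment 1, a visit on Days 2 to 10 falls in no window, however the unscheduled rule is read.
- After on-target Treatments 2 to 4 (Days 21, 42 and 63), the first three post-dose days are 22–24, 43–45 and 64–66. These fall inside the Visit 2, 3 and 4 windows, so here it is the unscheduled rule that removes the values, if it applies to vital signs.
- If it does not apply, Section 8 still keeps only the visit closest to the target day. With on-target dosing that is the treatment visit, and the unscheduled reading still drops out.

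**5. Treatment visits without treatment**

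Subjects who have cleared attend but are not treated, and visits where a reaction prevents treatment are recorded as unscheduled. If the Section 8 rules carry over, neither contributes vital signs to the treatment-visit rows.

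**6. What the planned tables can show**

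An abnormal reading at an in-window scheduled visit can appear as the minimum or maximum for that visit. That is one extreme value per treatment group and visit. It does not give the number of subjects affected, or whether the subject was normal at baseline.

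**The case against.** The strongest reply is that little is lost. SAP Section 5 promises listings of individual data. A fever, an infection or another unfavourable sign is an adverse event under Protocol 10.2.1, and SAP 10.2 tabulates TEAEs without visit windows. Local skin reactions, which trigger the mandatory unscheduled visit, have their own tables in SAP 10.3. All of this stands, and it limits the consequence. It does not supply the analysis in Protocol 12.4, because an abnormal reading need not be reported as an adverse event, and a listing gives no count by treatment.

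A second reply is that SAP 10.6 imports only the windows. The treatment-given and unscheduled rules are separate sentences in a section on efficacy, and the sentence after the unscheduled rule speaks of efficacy data. This is fair: their application to vital signs is a likely reading, not a stated one. The 48-hour gap and the missing shift analysis do not depend on it.

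A third is that Protocol 12.4 says only that changes will be identified and prescribes no count table. That is also true. The table proposed here is one reasonable way to meet the requirement; SAP 10.6 offers none.

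A reader might infer more: that only mean changes are planned, so that one abnormal subject would be averaged away, or that a fever would reach no vital-signs table. The documents do not support this. Observed values, minimum and maximum are planned, and an in-window scheduled fever would show there.

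A reader might also argue from pharmacology. Protocol 4.2 reports that after oral dosing in rats "cardiac waveform and function were adversely affected". In Protocol 4.3.1 the one quantifiable human plasma level was "slightly above the lower limit of quantitation 2 hours after VP-102 application but was not detectable at 6 and 24 hours". This does not help the case. No planned post-dose vital signs fall within hours of dosing, so the proposed table would not generally capture so brief an exposure. Protocol 4.2 also reports no systemic toxicity by the dermal route in animals.

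**Conclusion.** The point holds in two parts that need no inference. SAP 10.6 leaves out a safety analysis that Protocol 12.4 says will be done. Its windows also exclude Study Days 2 to 10, and with them the 48-hour vital signs of all 18 planned Part A subjects. A third part, the loss of readings from unscheduled and untreated visits, rests on reading the Section 8 rules as carried into SAP 10.6 by its cross-reference. The documents do not give the expected number of such visits, so that loss cannot be sized.

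The consequence is incomplete safety reporting. The excluded readings remain in listings, and reported events remain in the TEAE tables, so it would be wrong to conclude that a systemic reaction would go unseen. The study has no formal power calculation and all its comparisons are exploratory. Efficacy results and error rates are not touched, and no dose or clinical rule is involved. The change should be made because it is cheap and brings the SAP into line with the protocol.

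**What to change.** In SAP 10.6, add a table by treatment group giving the number and percent of Safety Population subjects with a normal baseline and an abnormal value (low and high shown separately) at any post-baseline in-clinic assessment. Do this for temperature and for heart rate. Include the Part A 48-hour visit, unscheduled visits and treatment visits without treatment. Use the baseline definition in SAP 8.2.

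State the reference ranges in the SAP before unblinding, since neither document gives them. Add a sentence that the Section 8 windows and visit exclusions do not apply to this safety summary. Keep the by-visit table as planned.

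The cost is one table, the reference ranges and a few sentences. It uses data already collected and needs no new assessments. If the sponsor decides against the analysis, the SAP should record and justify the departure from Protocol 12.4.

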10.7. Physical Examination

Physical examinations results will be displayed in a data listing. No summary tables of physical examination are planned.

10.8. Prior and Concomitant Medications

Prior and concomitant medication verbatim terms captured via the EDC system will be mapped to Anatomical/Therapeutic/Chemical (ATC) class and Preferred Names using the World Health Organization (WHO) Drug Dictionary Version September 2017.

Prior medications will be defined as those medications starting and ending before the first dose of study drug, or if the start date is missing and the end date is present and is prior to the first dose of study drug. Concomitant medications are any medications that are being taken on or after the first date of study medication. Prior and concomitant medications will be summarized for each treatment group by WHO ATC class and preferred name. These summaries will present the number and percent of subjects using each medication. Subjects may have more than one medication per ATC class and preferred name. At each level of subject summarization, a subject is counted once if one or more medications at that level is reported for the subject. Each summary will be ordered by descending order of incidence of ATC class and preferred term.
